Justification	
Covid-19 has enormous socio-economic consequences worldwide. Africa remains the continent least affected, despite the poverty level of its population and the fragility of its health systems. In inter-tropical African countries with high malaria prevalence, low prevalence of COVID-19 is reported.
 
According to some studies, the high prevalence of malaria in sub-Saharan Africa could play a role in protecting against the severity of COVID-19 in endemic areas. However, scientific evidence for the physiological role of this "trained" immunity has not been established. We wish to undertake this study to elucidate this hypothesis.

Objectives	
The main objective is to assess whether the immunity conferred by Plasmodium protects against severe forms of COVID-19. This will be achieved by comparing anti-plasmodium antibody levels in severe and non-severe COVID-19 cases.
 
The secondary objectives are :
 
▪ Comparing the cellular response to malaria between severe and non-severe COVID-19 cases▪ Compare the proportions of acute malaria infection between severe and non-severe cases of COVID-19 using the Thick Gout (TG) and Rapid Diagnostic Test (RDT).▪ Describe the clinical features and status of severe and non-severe cases of COVID-19 with and without malaria exposure▪ Evaluate the modulatory impact of existing antimalarial immunity on the strength of humoral and cellular immune responses to SARS-COV-2 in severe and non-severe cases of COVID-19

PROTOCOL: MALARIA AS A PROTECTIVE FACTOR AGAINST SEVERE COVID-19 IN THE DEMOCRATIC REPUBLIC OF CONGO

	
 ▪ Compare the SARS-CoV-2-specific cellular immune response between severe and non-severe cases ▪ Evaluate the modulatory impact of antimalarial immunity on trained immunity using specific stimulations of antiviral receptors in the innate immune system.
Methodology	Observational, multicenter, matched case-control study. The study will compare anti-plasmodium antibody levels between severe and non-severe cases of COVID-19.
Study population	The study will be carried out in four COVID-19 treatment centers for the recruitment of severe cases (cases). For each case, two controls will be recruited from the community based on the following concordance criteria: 
 ▪ Place of origin: same Health zone ▪ Gender ▪ Maximum 5-year age difference
Inclusion criteria	
For cases :
 
 ▪ Must be at least 18 years old ▪ PCR-confirmed SARS-CoV-2 infection within 72 hours of inclusion. ▪ Have given informed consent to participate in the study. ▪ Diagnosed as severe COVID-19 according to the following criteria: 
 ○ Clinical signs of pneumonia: fever, cough, dyspnea or crepitations AND ○ With at least one of the following : 
 ▪ Respiratory rate > 30 cycles/min OR ▪ Severe respiratory distress or SpO₂ < 90% on room air ▪ Admission to a care unit for COVID-19

PROTOCOL: MALARIA AS A PROTECTIVE FACTOR AGAINST SEVERE COVID-19 IN THE DEMOCRATIC REPUBLIC OF CONGO

	
 ▪ Have lived in the health zone for at least 6 months 
For witnesses :
 
 ▪ Must be at least 18 years old ▪ PCR-confirmed SARS-CoV-2 infection within 72 hours of inclusion. ▪ Have given informed consent to participate in the study ▪ Diagnosed as a non-severe COVID-19 case according to the following criteria: 
 ○ Be asymptomatic OR ○ Be symptomatic, but without any signs of severe pneumonia: 
 ▪ Respiratory rate > 30 cycles/min OR ▪ Severe respiratory distress or $SpO_2 < 90\%$ on room air ▪ Not to be admitted to a care unit for COVID-19. ▪ Have lived in the study area for at least 6 months
Exclusion criteria	
 ▪ The subject has a contraindication to venipuncture, determined by clinical judgment ▪ The subject is vaccinated against SARS-CoV-2 ▪ The subject has already been infected with SARS-CoV-2 in the past and now presents with reinfection.
Sample size	
300, including 100 cases and 200 controls:
 
Power is calculated by simulation. Power is calculated for different effect sizes (i.e. difference in anti-plasmodium antibody levels between cases and controls).

Calendar	
 ▪ Protocol drafting: February-May 2021 ▪ Ethics committee submission and approval: June 2021 ▪ Formation of study team: July 2021

PROTOCOL: MALARIA AS A PROTECTIVE FACTOR AGAINST SEVERE COVID-19 IN THE DEMOCRATIC REPUBLIC OF CONGO

	
▪ Data collection : July 2021 - December 2021▪ Data analysis: as soon as samples are received - March 2022▪ Presentation of results: May 2022
--	---

PROTOCOL: MALARIA AS A PROTECTIVE FACTOR AGAINST SEVERE COVID-19 IN THE DEMOCRATIC REPUBLIC OF CONGO

LIST OF ABBREVIATIONS AND ACRONYMS

AMA-1	Apical Membrane Antigen 1
COVID-19	Corona virus disease 2019
CSP	Circum Sporozoite Protein
CRF	Case Report Form' (data collection form, observation notebook)
CRC	Clinical Research Center
CTCo	COVID-19 processing center
ELISA	Enzyme-Linked Immunosorbent Assay
FM	Thin smear
GE	Thick drop
GLURP	Glutamat Rich Protein
IC	Investigator Coordinator
IC(F)	Informed Consent (Form)' - Formulaire de Consentement Eclairé
IC	Confidence interval
IFN- γ	Interferon gamma
IgG	Immunoglobulin G
INRB	National Institute for Biomedical Research
HbA1	glycated haemoglobin
MSP-1	Merozoite Surface Protein 1
WHO	World Health Organization
Pf	Plasmodium falciparum
PBMC	peripheral blood mononuclear cell
GROUND FLOOR	Democratic Republic of Congo

PROTOCOL: MALARIA AS A PROTECTIVE FACTOR AGAINST SEVERE COVID-19 IN THE DEMOCRATIC REPUBLIC OF
CONGO

RT-PCR	Reverse transcription polymerase chain reaction
SARS-CoV-2	Severe Acute Respiratory Syndrome Coronavirus 2
TDR	Rapid diagnostic test
ZS	Health Zone

1 INTRODUCTION

Corona virus disease 2019 (COVID-19) is caused by a new virus, severe acute respiratory syndrome corona virus 2 (SARS-CoV-2), which was first reported in a group of pneumonia patients in the Chinese city of Wuhan on December 31, 2019 [1]. The epidemic that began in Wuhan then spread very rapidly worldwide and became a pandemic declared by the World Health Organization (WHO) on March 11, 2020 [2]. COVID-19 in its first wave and the current second wave is having enormous socio-economic consequences worldwide. The disease is therefore a major public health problem. According to data compiled by the American Johns-Hopkins University, up to May 2, 2021, more than 150 million people have tested positive for Covid-19 worldwide, and more than 3 million have died from the disease [3].

No continent is spared from COVID-19, although Africa remains the least affected despite its population's level of poverty and the fragility of its health systems, which predispose it to high mortality. However, the realities on the ground are proving to be contrary to all predictions [4]. Although there are many factors that can influence the transmission of COVID-19, including demographics, socio-cultural aspects, the young age of the population, the warm climate and genetics, this does not fully explain why the mortality rate is lower than those observed in Europe and the USA [5-7].

According to data compiled by the American Johns-Hopkins University on March 2, 2021, Africa has around thirty million confirmed cases of COVID-19 and 104,384 deaths, with proportions varying from region to region. There is a high prevalence of COVID-19 in regions with low malaria prevalence, such as the Maghreb region, notably Morocco with 513,314 confirmed cases and Tunisia with 318,236 cases, and South Africa with 159,2626 cases. Conversely, in inter-tropical African countries with high malaria prevalence, low prevalence of COVID-19 has been reported, perhaps due in part to under-diagnosis. This is notably the case in Nigeria, with 9,7478 confirmed cases, and the Democratic Republic of Congo (DRC), with over 29,000 cases [8].

The DRC is the second malaria-endemic country in Africa after Nigeria, and malaria remains the main cause of morbidity and mortality. At the time of writing on May 2, there are over 18 million cases and more than 18,000 deaths per year [9].

The prevalence of malaria in the DRC varies according to geographical location and depends on individual and community diversity; incidence is generally high in rural areas [10]. The DRC has a population of over 90,000,000, with a precarious health system and lax protective measures. However, according to the COVID-19 DRC epidemiological report of March 5, 2021, there are around 712 deaths due to COVID-19, despite effective circulation of the virus in the population. 75% of cases are concentrated in the capital Kinshasa, which is the

PROTOCOL: MALARIA AS A PROTECTIVE FACTOR AGAINST SEVERE COVID-19 IN THE DEMOCRATIC REPUBLIC OF CONGO

epicenter of COVID-19, where malaria is meso-endemic, with a lower prevalence in urban areas compared with peri-urban areas [11].

Several recent studies have demonstrated that the "early" innate immune response can be shaped differently by prior exposure to immune stimuli. However, little is known about how endemic micro-organisms such as *Plasmodium*s and helminths shape the innate immune response and direct the reactivity and efficacy of the immune response as a whole [12, 13].

The high prevalence of malaria in sub-Saharan Africa has been assumed to confer possible protection against the severity of COVID-19 in endemic areas [14]. Our preliminary *in vitro* data indicate that prior and repetitive stimulation of anti-parasitic innate immune receptors induces an immune entrainment mechanism, stimulating the type I IFN response while attenuating the release of pro-inflammatory cytokines during SARS-CoV-2 infection (prof. [name] et al., unpublished results). According to several studies, high IFN type I release in conjunction with low induction of pro-inflammatory cytokines correlates with a less severe clinical course of COVID-19. This suggests a potential protective effect against COVID-19 virus in malaria-endemic areas [15, 16].

However, scientific evidence for the physiological role of this "trained" immunity is not established. This is why we are undertaking this study to shed light on a possible protective role of malaria in patients testing positive for COVID-19. The aim of this study is to show whether the immunity conferred by repeated *Plasmodium* infections protects against severe forms of COVID-19.

2 STUDY OBJECTIVES

The main objective is to investigate whether the immunity conferred by *Plasmodium* protects against severe forms of COVID-19. This will be achieved by comparing anti-plasmodium antibody levels in severe and non-severe COVID-19 cases.

The secondary objectives are :

- Comparing the cellular response to malaria between severe and non-severe COVID-19 cases
- Compare the proportions of acute malaria infection between severe and non-severe cases of COVID-19 using the thick drop (GE) and rapid diagnostic test (RDT).
- Describe the clinical features and status of severe and non-severe cases of COVID-19 with and without malaria exposure

PROTOCOL: MALARIA AS A PROTECTIVE FACTOR AGAINST SEVERE COVID-19 IN THE DEMOCRATIC REPUBLIC OF CONGO

- Evaluate the modulatory impact of existing antimalarial immunity on the strength of humoral and cellular immune responses to SARS-COV-2 in severe and non-severe cases of COVID-19
- Compare the SARS-COV-2-specific cellular immune response between severe and non-severe cases
- Evaluate the modulatory impact of antimalarial immunity on trained immunity using specific stimulations of antiviral receptors in the innate immune system.

3 VARIABLES OF INTEREST

3.1 PRIMARY VARIABLES OF INTEREST :

The study's primary variable of interest is the level of anti-malarial antibodies in severe and non-severe COVID-19 cases. This level will be assessed by measuring the concentration of IgG against Circum Sporozoite Protein (CSP) using the Luminex- MAGPIX.

3.2 SECONDARY VARIABLES OF INTEREST :

- Anti-malarial IgG antibody levels against other antigens: AMAI, CSPM, GLURP, Pf/RESA55, as well as IgM
- The cellular response against malaria between severe and non-severe COVID-19 cases, measured by IFN- γ ELISPOT
- Proportions of acute malaria infection between severe and non-severe cases of COVID-19 using the Thick Gout (TG) and Rapid Diagnostic Test (RDT).
- Clinical characteristics and clinical status of severe and non-severe cases of COVID-19 with and without malaria
- SARS-COV-2 specific cellular and humoral immune response of severe and non-severe cases
- Antiviral cytokine release levels, measured by ELISA and flow cytometry, of peripheral blood monocyte cells (PBMC) from controls and patients with acute malaria infection (according to GE and TDR).

4 DESIGN OF THE STUDY

An observational, multicenter, matched-case-control study. The study will compare the quality of malaria immunity in severe and non-severe cases of COVID-19.

PROTOCOL: MALARIA AS A PROTECTIVE FACTOR AGAINST SEVERE COVID-19 IN THE DEMOCRATIC REPUBLIC OF CONGO

The study will be carried out in four Treatment Centers (CTCo) to recruit severe cases (cases). Controls will be recruited from the Health Zone (ZS) on the basis of the same characteristics as the cases, taking into account age (upper and lower 5-year intervals), sex and ZS of origin.

5 METHODS

5.1 STUDY ENVIRONMENT AND POPULATION.

This case-control study will be carried out in the Republic of Congo, in the city of Kinshasa, the epicenter of COVID-19. Kinshasa is a malaria-endemic zone, with a lower prevalence of malaria in urban areas than in peri-urban areas. In fact, the city of Kinshasa is structured into four health districts and sixteen hospital centers, spread across the thirty-five Health Zones for the management of COVID-19.

The study will consist of cases and controls:

- The cases will be severe COVID-19 cases, and will comprise hospitalized patients recruited from COVID-19 Treatment Centers (CTCOs).
- Controls will consist of asymptomatic or symptomatic cases without signs of severity. For each case, two controls will be recruited after being matched in terms of age, sex and Health Zone of origin.

5.1.1 INCLUSION CRITERIA

To be eligible, study patients must meet the following criteria:

For cases :

- Must be at least 18 years old
- RT-PCR-confirmed SARS-CoV-2 infection no more than 72 hours prior to inclusion.
- Have given their informed consent or that of their guardian/representative to participate in the study.
- Diagnosed as severe COVID-19 according to the following criteria:
 - Clinical signs of pneumonia: fever, cough, dyspnea or crepitations
AND
 - Presenting at least one of the following signs:
 - Respiratory rate > 30 cycles/min
OR
 - Severe respiratory distress or SpO2 < 90% on room air

PROTOCOL: MALARIA AS A PROTECTIVE FACTOR AGAINST SEVERE COVID-19 IN THE DEMOCRATIC REPUBLIC OF CONGO

- Being admitted to a care unit for COVID-19
- Have lived in the health zone for at least 6 months

For witnesses :

- Must be at least 18 years old
- PCR-confirmed SARS-CoV-2 infection within 72 hours of inclusion.
- Have given informed consent to participate in the study
- Diagnosed as a non-severe COVID-19 case according to the following criteria:
 - Be asymptomatic

OR

 - Symptomatic, but no signs of severe pneumonia
 - Respiratory rate > 30 cycles/min

OR

 - Severe respiratory distress or SpO2 < 90% on room air
- Not to be admitted to a care unit for COVID-19.
- Have lived in the study area for at least 6 months

5.1.2 Exclusion criteria

To be eligible, study patients must not meet the following criteria for cases and controls:

- The subject has a contraindication to venipuncture, determined by clinical judgment
- The subject is vaccinated against SARS-CoV-2
- The subject has already been infected with SARS-CoV-2 in the past and now presents with reinfection.

5.1.3 RECRUITING SEVERE CASES

Severe cases will be recruited from four state CTCOs. The choice of CTCOs takes into account the frequency of severe cases and the geographical distribution of malaria in the city of Kinshasa. The centers are as follows:

- Saint Joseph Hospital
- Kinkole General Hospital
- Cliniques Universitaires de Kinshasa
- Ngaliema Clinics

PROTOCOL: MALARIA AS A PROTECTIVE FACTOR AGAINST SEVERE COVID-19 IN THE DEMOCRATIC REPUBLIC OF CONGO

After political and administrative authorizations have been obtained by a qualified member of the research team, all severe cases in the care units of the selected centers will be investigated for their eligibility for the study, and then invited to participate and give informed consent.

5.1.4 RECRUITING WITNESSES

For each case, two controls will be recruited in the Health Zone from which the severe cases originated. The Health Zone nurse assigned to the COVID-19 response and the investigator assigned to the site will record the witness information in the register of RT-PCR-positive cases for COVID-19.

The first two controls on the linear list with a COVID-19 RT-PCR test result of 72 hours or less and with the same characteristics will be contacted and invited to take part in the study. If participation is refused, the next person on the list will be taken. Controls must be matched to the case on the basis of the following concordance criteria:

- Age: +/- 5 years relative to case age
- Gender: same as case
- Place of origin: same health zone as the case

During the follow-up home visit planned by the ZS for the non-severe COVID19 patient, the investigator will accompany the ZS nurse supervisor, and the study will thus be introduced to the patient. Once informed consent has been obtained, the questionnaire and blood sample will be taken during the same visit. In compensation for their time, the controls will receive masks and soap to limit the spread of the virus in their environment.

5.1.5 SAMPLE SIZE AND STATISTICAL POWER

The sample size is 300 participants, made up of 100 cases and 200 controls. Sample power is calculated according to the following assumptions:

- Median antibody titers in controls are estimated at 898 mfi (*mean fluorescence intensity*). This estimate is based on a previous study in which antibody titres against CSP were determined by the same Luminex technology in a malaria-endemic context [17].
- The logarithm of the anti-malarial anti-CSP antibody levels of the controls is normally distributed, with a mean of 6.8 and a standard deviation of 1.
- The logarithm of malaria antibody levels in cases is normally distributed with a standard deviation of 1.
- For each case, two matched controls are recruited.

PROTOCOL: MALARIA AS A PROTECTIVE FACTOR AGAINST SEVERE COVID-19 IN THE DEMOCRATIC REPUBLIC OF CONGO

- The correlation between the logarithm of anti-malarial antibody levels in cases and matched controls is 0.7.

The data collected will be analyzed using conditional logistic regression with a two-tailed test at the 5% significance level.

Power is calculated for different effect sizes (i.e. difference in malaria antibody levels between cases and controls). The table below shows the power for different effect sizes, or rather design effects. With a sample size of 300, the study is able to detect a 17% difference in median antibody titres with 80% power, which is considered clinically relevant.

Mean of logarithm of anti-malarial antibody levels in controls	Average of the logarithm of anti-malarial antibody levels in cases	Median malaria antibody levels of controls	Median malaria antibody levels of cases	Power
6.8	6.7	898	812	0.3
6.8	6.69	898	804	0.35
6.8	6.68	898	796	0.4
6.8	6.67	898	788	0.48
6.8	6.66	898	781	0.53
6.8	6.65	898	773	0.6
6.8	6.64	898	765	0.65
6.8	6.63	898	757	0.7
6.8	6.62	898	750	0.76
6.8	6.61	898	742	0.81

PROTOCOL: MALARIA AS A PROTECTIVE FACTOR AGAINST SEVERE COVID-19 IN THE DEMOCRATIC REPUBLIC OF CONGO

6.8	6.6	898	735	0.83
6.8	6.59	898	728	0.87
6.8	6.58	898	721	0.9
6.8	6.57	898	713	0.93
6.8	6.56	898	706	0.94
6.8	6.55	898	699	0.96

In conclusion, with a sample size of 300, the study is able to detect a 17% difference between median antibody titers with 80% power.

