2. STUDY DESIGN AND OBJECTIVES

2.1. DESIGN

An observational, multi-centre, matched case-control study. The study will compare the quality of malaria immunity in severe and non-severe cases of COVID-19. The study will be conducted in four Treatment Centres (CTCo) to recruit severe cases (cases). Controls will be recruited at the Health Zone (HZ) level on the basis of the same characteristics as the cases, taking into account age (upper and lower 10 years), sex and HZ of origin.

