5. POPULATION OF THE STUDY

This case-control study will be conducted in the Republic of Congo in the city of Kinshasa, the epicentre of COVID-19. Kinshasa is a malaria endemic area, the distribution of malaria prevalence is lower in urban areas compared to peri-urban areas. In fact, the city of Kinshasa is structured in four health districts and sixteen hospitals, distributed in the thirty-five health zones for the management of COVID-19.

The study consists of cases and controls: For each case, a control will be recruited.

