5.2. DESCRIPTION OF

Controls will consist of asymptomatic or symptomatic cases without signs of severity. For each case, a control will be recruited after being matched in terms of age (plus or minus 10 years), gender and

Health Zone of origin. The time to recruit a control is up to 10 weeks after case recruitment.

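### The only power calculation (80% for a 17% difference) assumes two controls per case, but the SAP recruits one and gives no case count; at 100 pairs power is about 64–69%, at 150 pairs about 83–85%

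*Protocol*

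**What the plan says.** **Protocol.** Section 5.1.5 fixes the size and ratio: "The sample size is 300 participants, made up of 100 cases and 200 controls", and among the power assumptions, "For each case, two matched controls are recruited". The synopsis and sections 5.1 and 5.1.4 also specify two controls per case. Section 5.1.4 sets the age match: "Age: +/- 5 years relative to case age"; the synopsis and section 4 agree. The correlation assumption is "The correlation between the logarithm of anti-malarial antibody levels in cases and matched controls is 0.7", with no source given. From these inputs section 5.1.5 tabulates power for 16 effect sizes and concludes: "With a sample size of 300, the study is able to detect a 17% difference in median antibody titres with 80% power". It describes that difference as clinically relevant.

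**SAP.** Section 5 says: "For each case, a control will be recruited". Section 5.2 repeats the ratio and widens the age match: "For each case, a control will be recruited after being matched in terms of age (plus or minus 10 years), gender and" (the sentence ends with the third matching factor, which is the same as in the protocol). It also allows up to 10 weeks after the case to find the control. Section 2.1 likewise has "taking into account age (upper and lower 10 years), sex and HZ of origin". Nowhere does the SAP give a number of cases, a total or a power figure, and it does not explain the change from the protocol.

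**The concern.** The matching ratio, the age range and the number of matched sets define the primary comparison. The two documents disagree on the first two, and the SAP is silent on the third. All 16 power values assume two controls per case, so none applies to the SAP's design.

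What is at stake is how the result will be read. If the study has 100 pairs and finds no association, a report that quotes 80% power for 17% would overstate how firmly that difference had been excluded. The chance of missing it would be about 31–36%, not about 20%. Type I error is not affected, because conditional logistic regression is valid for either ratio.

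**Working it through.** **Inputs from protocol 5.1.5.** The SD of log titre is 1 in both groups, the case–control correlation ρ is 0.7, the test is two-sided at 5%, and there are n = 100 cases with m = 2 controls each. The correlation between the two controls of one case is not stated. I take it as 0.7 as well; this affects only the 1:2 figures.

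**Effect size.** Let d be the difference in mean log titre. Exactly 17% gives d = −ln(0.83) = 0.1863. The nearest table row (case mean 6.61, stated power 0.81) gives d = 6.80 − 6.61 = 0.19, and 1 − exp(−0.19) = 17.3%. Both are carried through.

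**Formula.** For the case value minus the mean of its m controls, averaged over n sets:

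SE = √[(1 − ρ)(1 + 1/m)/n], and power = Φ(d/SE − 1.96).

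**Step 1: reproduce the protocol's figure (1:2, n = 100).** SE = √(0.3 × 1.5/100) = 0.0671.
- d = 0.1863: Φ(2.778 − 1.96) = 0.793, against the stated 0.80.
- d = 0.19: Φ(2.832 − 1.96) = 0.81, against the stated 0.81.

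The formula is within about 0.03 of the stated power in all 16 rows. The protocol's calculation is therefore reproduced, and it clearly belongs to the 1:2 design.

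**Step 2: one control per case.**
- 100 pairs: SE = √(0.3 × 2/100) = 0.0775. Power = Φ(2.405 − 1.96) = 0.672 for d = 0.1863 and Φ(2.453 − 1.96) = 0.689 for d = 0.19.
- 150 pairs: SE = √(0.6/150) = 0.0632. Power = 0.838 and 0.852.

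**Step 3: check by simulating the planned analysis.** Conditional logistic regression was simulated with 20,000 data sets per setting. Each cell shows d = 0.1863 / d = 0.19.

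| Design | Formula | Wald test | Likelihood-ratio test |
|---|---|---|---|
| 100 cases, 1:2 | 0.793 / 0.809 | 0.785 / 0.798 | 0.795 / 0.807 |
| 100 pairs, 1:1 | 0.672 / 0.689 | 0.643 / 0.663 | 0.665 / 0.684 |
| 150 pairs, 1:1 | 0.838 / 0.852 | 0.826 / 0.840 | 0.837 / 0.851 |

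**Step 4: difference detectable with 80% power**, d = (1.960 + 0.8416) × SE.
- 100 cases, 1:2: 0.188, or 17.1%.
- 100 pairs: 2.8016 × 0.0775 = 0.217, or 19.5%. With the Wald test, simulated power reaches 0.80 at about d = 0.223, or 20.0%.
- 150 pairs: 0.177, or 16.2%.

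**Step 5: pairs needed for 80% power**, (1.960 + 0.8416)² × 0.6/d². This is 7.849 × 0.6/0.0347 = 135.6, so 136 pairs for exactly 17%, and 7.849 × 0.6/0.0361 = 130.5, so 131 pairs for 17.3%. With the Wald test at exactly 17%, about 140 pairs are needed (simulated power 0.797 at 140).

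**Step 6: the correlation, as an assumption only.** The value 0.7 stands in the protocol, where matching is within 5 years. A wider age range would not be expected to raise it, but the documents do not show how much it would change. For scale, 100 pairs at d = 0.19 give formula power of about 0.56 if ρ were 0.6 and 0.48 if it were 0.5. Neither value comes from the documents, and the conclusion does not rest on them.

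**The case against.** **Nothing in protocol 5.1.5 is miscalculated.** This is true. The fault is a conflict between documents, and the quoted sentence goes wrong only when it is carried over to the SAP's design.

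**The shortfall is one of two branches.** This also stands. Section 5.1.5 ties its claim to a total of 300, and 300 people as 150 pairs would keep power above 80%. The documents do not choose between 100 and 150 pairs, so a loss of power is possible but not shown. What is shown is that the power of the SAP's design is not stated.

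**The SAP may follow a later design.** It adds antigen testing, urinary and intestinal parasites, and a 10-week window for controls, none of which is in this protocol. A revised sample size may exist elsewhere, and the SAP refers to the protocol for details of conduct. That makes a deliberate change more likely than loose wording, but it does not supply the missing figure. A reader who follows the reference reaches a calculation for a different ratio.

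**The harm is prospective.** The SAP repeats no power claim, the model is valid either way, and the repair is mostly wording. This limits the harm to how the result is interpreted, but the planned report rests on the SAP, so the SAP is where the figure has to be put right.

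**Conclusion.** The concern holds. The only power calculation in the documents is correct for 100 cases with two controls each and does not describe the one-to-one design in the SAP. If cases stay at 100, power for a 17% difference is about 64–69%, and 80% power is reached only at a difference of about 19.5–20%. At 150 pairs power is about 83–85% and there is no shortfall. About 131–140 pairs are needed for 80%, depending on the test and on whether 17% is taken as exact or as the table row.

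These figures rest on the protocol's own SD of 1 and correlation of 0.7, and on no loss of pairs. The last is optimistic under 1:1 matching. A control who becomes severe by Day 7 is removed (protocol 5.2.2.1) and participants with missing data are excluded (SAP 11). Losing either member of a pair removes that pair from the conditional likelihood, whereas a set with two controls can survive the loss of one.

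**What to change.** 1. Reconcile the matching ratio (1:2 or 1:1), the age range (5 or 10 years) and the number of cases across the protocol and SAP, and record the reason for any change.
2. Restate in the SAP the power and detectable difference for the design actually used. For 100 pairs: about 64–69% power for 17%, and 80% power for about 19.5–20%. For 150 pairs: about 83–85% for 17%. If the design is still 1:2 with 100 cases, correct SAP sections 5 and 5.2; the protocol's 80% then stands on its stated assumptions.
3. Optionally, show power at lower correlations and with some pairs lost, labelled as assumptions.

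The cost is wording in both documents and one rerun of the existing simulation with a single control per case. No extra participants are required. The drawback is a less favourable stated power if 100 pairs is the design.
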